## Schema

# Low Dose Tamoxifen for Radiation-Induced Breast Cancer Risk Reduction

230 patients will be randomized 1:1 to take a tablet containing 5mg tamoxifen (TAM) versus a placebo of equal size and shape daily for two years. The primary endpoint is mammographic density, which will be measured at baseline and on an annual basis (at Year 01 and 02). Blood and urine collections will also be scheduled annually for measurement of circulating markers of efficacy and safety. Normal breast tissue will be sampled before and after the two-year treatment course for measurement of tissue-based efficacy markers (breast tissue sampling by RPFNA no longer collected from patients).

[figure not shown]
## 1.0 OBJECTIVES

- 1.1 To determine the impact of a two-year course of low-dose tamoxifen administered at 5mg per day on surrogate endpoint biomarkers of breast cancer (BC) risk, including:
  - mammographic breast density (MBD), an established radiographic biomarker of BC risk,
  - cytomorphology and proliferative index, tissue biomarkers closely linked to BC risk, and
  - sex steroid hormones and insulin growth factors, circulating biomarkers of BC risk.
- 1.2 To establish safety and tolerability of this low-dose tamoxifen regimen, assessing both objective measures (lipid profiles, clotting factors and bone metabolism markers) and patient-reported outcomes.
- 1.3 To examine the modifying effect of demographic, clinical, and molecular characteristics on the risk: benefit ratio from this two-year low dose tamoxifen intervention.
- 1.4 To explore the relationship between this low-dose tamoxifen regimen and clinical measures of efficacy (new breast cancer and DCIS diagnoses) and toxicity (thromboembolic events, reports of hot flashes and gynecological symptoms, liver function abnormalities, and other cancer diagnoses).

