These concerns led some investigators in Italy to evaluate lower doses of tamoxifen in a four-arm double-blind placebo-controlled randomized trial of 210 healthy postmenopausal women, hoping to find a dose that would be better tolerated yet still efficacious for breast cancer risk reduction [41]. Participants were randomized to one of four treatment arms: 1) tamoxifen at 1 mg/day and a weekly placebo, 2) a daily placebo and tamoxifen at 10 mg/week, 3) tamoxifen at 5 mg/day and a weekly placebo, or 4) both daily and weekly placebos for 12 months. Plasma insulin-like growth factor 1 (IGF-1), which is positively correlated with BC risk, was the primary endpoint, evaluated before and after the 12-month treatment. Secondary endpoints included MBD, IGF binding protein-3 (IGFBP-3), fibrinogen, antithrombin-III (AT3), C-telopeptide (CTX), and endometrial proliferation assessed by Pipelle biopsy. MBD is positively correlated with BC risk, while IGFBP-3 is negatively correlated with BC risk. Along with IGF-1, they served as surrogate endpoints of efficacy. Fibrinogen and AT3 are markers of clotting risk, CTX, which is positively correlated with bone resorptive activity, is a marker for osteoporosis risk, and endometrial proliferation is a marker of uterine cancer risk. Collectively, these were safety endpoints in the trial. The investigators reported a significant decrease in IGF-1 in all tamoxifen arms relative to placebo ( $p = 0.005$ ), with the greatest change observed in the 5 mg/day treatment arm ( $p = 0.019$ ). Low-dose tamoxifen also lowered MBD and increased IGFBP-3, with optimal effects observed in the 5 mg/day arm. These findings all consistently suggest that 5 mg/day dosing is the most effective dose schedule of low-dose tamoxifen. No significant change was observed with CTX, suggesting that low-dose tamoxifen does not adversely affect bone health. Interestingly, a significant decrease in AT3 ( $p = 0.006$ ), particularly with the 5 mg/day dose schedule, was also seen, suggesting that low-dose tamoxifen may be associated with a lower clotting risk than even placebo. While there was an association between low-dose tamoxifen and endometrial thickness, no association was found with endometrial proliferation measured with Ki67 expression. In fact, Ki67 was lowest in patients receiving the 5 mg/day dose, suggesting that low-dose tamoxifen at that dose would likely not be associated with an increased risk of endometrial carcinoma as is observed with standard dose tamoxifen. Also, menopausal symptoms were not

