In summary, because the dose that we will be administering will be 5 mg per day rather than 20 mg per day, we expect no significant increase in these adverse events in the treatment group compared to the placebo group. In addition, the median age of the patient cohort from which trial participants will be drawn is 36 years old, while the adverse effects associated with the 20 mg per day of tamoxifen were only significantly elevated above placebo among women who were 50 years old or older at the time of treatment initiation. However, precautions will be taken, nevertheless (see Section 8.2 for guidelines regarding adverse event reporting and for data safety monitoring). In addition, women with childbearing potential will be warned that they should avoid pregnancy while taking study medication and for two months after discontinuation.

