**Objective safety measures:**

**Adverse events.** The number of grade 2-4 toxicities observed will be tabulated by treatment arm. Differences by treatment arm will be evaluated using Fisher exact tests.

**Biomarkers.** Total cholesterol, low and high density lipoprotein, triglycerides, anti-thrombin III enzymatic assay (for clotting propensity), and serum bone-specific alkaline phosphatase (BSAP, for bone formation) and urine N-telopeptides (NTX, for bone resorption) measurements will be treated as continuous variables. Transformed to normality as appropriate, the linear mixed effects model will be applied, using the unstructured mean model using and linear in time model, to assess the effects of low dose tamoxifen on these measurements over time.

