**Adverse events:** We assume the rate of grade 2-4 toxicities in the placebo group to be low, at 0.5%. At the end of the study, with 94 women in each arm (accounting for 10% attrition per year), the study will have at least 80% power to detect an adverse event rate of 9.1% in the low dose tamoxifen group based on Fisher’s exact test and Type I error=0.05.

**Adherence to therapy:** We will examine the difference in adherence rates of the treatment groups by comparing the percent of pills taken across 8 time points. With 115 women at baseline per arm, assuming a constant adherence rate of 90% in the placebo group and a between-measurement correlation of 0.6 and 2-sided alternative, there will be 80% power to detect an adherence rate of about 77% in the low dose tamoxifen group.

**Voluntary withdrawals:** If the proportion of patients in the placebo arm who withdraws voluntarily by the end of the study is 10%, then with 115 women in each arm at baseline, assuming type I error=0.05, the study will have 80% power to detect a significant difference in the voluntary withdrawal rate in the low dose tamoxifen group if the withdrawal rate in the intervention group is about 28%.

**Safety biomarkers:** We focus here on total cholesterol (TC), anti-thrombin-III (AT-III), bone-specific alkaline phosphatase (BSAP), and urine N-telopeptide crosslinks (NTX). With the proposed sample sizes, the detectable effect size (described earlier) is 0.34. A relatively small % change in mean levels is detectable for TC and AT-III but larger % changes are needed to detect a significant treatment difference at t2 for BSAP and NTX.

Outcome	Assumed levels at t0 for Placebo and Low dose Tamoxifen groups	Detectable levels at t2 (80% power) for Low dose Tamoxifen group	
	Mean ± SD	Mean	Relative % change (from t0)

TC* (mg/dL)	199 ± 45	214.3	8% ↑
AT-III** (%)	100 ± 13.3	95.5	5% ↓
BSAP  (µg/L)	7.7 ± 4.5	6.2	20% ↓
NTX  (nM BCE/mM)	24.4 ± 16.1	18.9	23% ↓

\* Mean obtained from [111], sd obtained from [112]

\*\* per ARUP reference laboratory

Thus, we expect to be able to detect a 5-23% difference in the objective safety biomarkers proposed as secondary endpoints.

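### Aim 2 sets out to establish safety and tolerability, but the plan has only tests for a difference, with no criterion for 'established' and no interval on excess harm

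*Combined protocol and SAP*

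**What the plan says.** Objective 1.2 (Section 1.0) reads "To establish safety and tolerability of this low-dose tamoxifen regimen, assessing both objective measures", and Aim 2 in Sections 12.4 and 12.5 repeats the verb.

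For adverse events, Section 12.4 tabulates grade 2-4 toxicities by arm and then says "Differences by treatment arm will be evaluated using Fisher exact tests". Lipids, anti-thrombin III, BSAP and NTX go into linear mixed models "to assess the effects of low dose tamoxifen on these measurements over time". Withdrawals are compared by chi-square or Fisher's test. Adherence and symptoms are compared through longitudinal models of treatment differences.

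Section 12.5 sizes the toxicity comparison at 94 women per arm after attrition, with an assumed placebo rate of 0.5%, and claims "at least 80% power to detect an adverse event rate of 9.1% in the low dose tamoxifen group". For safety biomarkers it gives a detectable effect of 0.34 SD.

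Three other passages bear on the point:

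- Section 3.3 says of the adverse events known from 20 mg tamoxifen that "we expect no significant increase in these adverse events in the treatment group compared to the placebo group".
- Section 2.2 says of the earlier four-arm low-dose trial: "No significant change was observed with CTX, suggesting that low-dose tamoxifen does not adversely affect bone health".
- Section 10.0 says that toxicity outcomes will be reported for all eligible subjects.

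**The concern.** A test of no difference can show harm. It cannot show that harm is absent or small: the fewer the events and the noisier the measurement, the more easily the test is non-significant. If the objective is to establish safety, the analysis needs a stated limit on excess harm, or at least an interval showing how large an excess the data still allow. Aim 2 has neither.

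This matters because better tolerability at low dose is the rationale for the regimen, and the participants are young women without active cancer. The report could describe the regimen as safe while its data remain compatible with a sizeable excess of toxicity, or with a shift in clotting, bone or lipid markers that nobody has quantified.

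**Working it through.** **Inputs (Section 12.5).** Placebo grade 2-4 rate 0.5%; alpha 0.05; 115 women randomised per arm; 94 per arm after 10% yearly attrition (115 × 0.9 × 0.9 = 93.15). Sidedness is not stated for this test.

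**The plan's own figure.** The claim is at least 80% power for 0.5% v 9.1% at 94 per arm by Fisher's test. Power is the sum, over placebo counts x, of P(x) × P(tamoxifen count reaches the smallest significant value given x).

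- Two-sided Fisher: 75.4%
- One-sided Fisher: 85.7%
- Two-sided normal approximation: 79.2% pooled, 80.4% unpooled

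The figure therefore holds for a one-sided Fisher test, or roughly for a two-sided normal approximation, but not for a two-sided Fisher test. Both sidednesses are carried forward.

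**A smaller but real excess: 0.5% v 5%.** At 94 per arm, two-sided:

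| Placebo events x | P(x) | Smallest significant tamoxifen count | P(reaching it at 5%) | Product |
|---|---|---|---|---|
| 0 | 0.6243 | 6 | 0.3302 | 0.2061 |
| 1 | 0.2949 | 8 | 0.0985 | 0.0291 |
| 2 | 0.0689 | 10 | 0.0192 | 0.0013 |
| 3 | 0.0106 | 11 | 0.0073 | 0.0001 |

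The sum is 0.237, so 76.3% of trials are non-significant. The same calculation for the other cases gives:

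| Women per arm | Two-sided | One-sided |
|---|---|---|
| 94 | 76% non-significant | 62% non-significant |
| 115 | 63% non-significant | 49% non-significant |

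**What a non-significant table still allows.** With 94 per arm and 4 events on tamoxifen v 0 on placebo, two-sided Fisher p = 0.12. The Newcombe 95% interval for the risk difference runs from -0.4 to 10.4 percentage points.

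**Best possible result.** With no events among n women, the upper limit of the two-sided 95% interval is 1 - 0.025^(1/n). For n = 94 this is 3.8%; for n = 115 it is 3.2%. Both are well above the assumed placebo rate.

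**Safety biomarkers.** Taking the plan's 80% power at 0.34 SD, the implied standard error is 0.34 / (1.960 + 0.842) = 0.121 SD. The 95% half-width is 1.96 × 0.121 = 0.238 SD. With the SDs in Section 12.5:

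- total cholesterol: 0.238 × 45 = 10.7 mg/dL
- anti-thrombin III: 0.238 × 13.3 = 3.2 points
- BSAP: 0.238 × 4.5 = 1.1 µg/L
- NTX: 0.238 × 16.1 = 3.8 nM BCE/mM

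The plan could state these precisions but does not.

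**The case against.** **The documents contain no rule that p > 0.05 means safe.** This is correct. Section 12.4 writes an explicit decision rule for efficacy and none for safety. A reader might infer that a non-significant test is the planned route to a safety claim, and that a toxic drug would pass. The documents do not support that. In Section 3.3 the expectation of no significant increase is a forecast about the known 20 mg events, and it is followed by a promise of precautions. The bone statement in Section 2.2 is background on another trial. What stands is that no criterion is stated, in a protocol whose background does read non-significance as reassurance.

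**Harm limits do exist.** Section 6.4.1 sets numerical limits for grade 4 thromboembolism and endometrial cancer, and holds accrual for repeated unexpected grade 3-4 toxicity. Section 8.2.3 adds monthly committee review. It would be wrong to say that no bound on harm is planned. But these limits cover selected events during the trial. They do not quantify overall grade 2-4 toxicity, biomarkers or symptoms.

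**Low power is admitted.** Section 12.5 does so under Exploratory Aim 2, for the clinical events of objective 1.4. No such caveat is attached to Aim 2.

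**The 76% is one end of a range.** This is also correct. Sidedness is unstated, and reporting toxicity for all eligible subjects points towards 115 per arm. Calling 5% a tenfold rise leans on the assumed 0.5%. Two-sided, a tenfold rise from 1% would be missed in 27% of trials at 94 per arm and 16% at 115. The 4.5-point absolute excess is the fairer description.

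**The wording is ordinary for phase IIb, and safety is secondary here.** That limits the weight of the point but does not supply the missing criterion.

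**Conclusion.** The point holds as a gap between objective and analysis. Aim 2 claims to establish safety and tolerability, but nothing in Sections 12.4 or 12.5 defines when that has been achieved or bounds the excess that remains possible. A non-significant toxicity test would be weak evidence: 49% to 76% of trials would miss a true 5% v 0.5%, and zero events in 94 women would still leave 3.8% within the interval.

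These figures rest on the plan's assumed placebo rate and change considerably with it. The 5% comparison rate is illustrative; the documents name no acceptable excess. The biomarker half-widths assume that the plan's 0.34 SD is right.

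The point does not touch the primary density endpoint or show that safety monitoring is inadequate. It concerns what the final report may conclude, and the change is worth making because it costs little.

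**What to change.** 1. In objective 1.2 and in the Aim 2 headings of Sections 12.4 and 12.5, replace *establish* with *estimate*.
2. In Section 12.4, Aim 2, make the between-arm difference with its two-sided 95% confidence interval the reported safety result: an exact or score interval for risk differences in toxicity, and model-based intervals for safety biomarkers and symptom scores. Name the interval method in advance, because methods can disagree at low counts. For 5 v 0 events at 94 per arm, two-sided Fisher p = 0.059, but the Newcombe lower limit is +0.4 points.
3. Word the safety conclusion as the largest excess that the interval does not exclude, and state that p > 0.05 will not be reported as evidence of safety.
4. In Section 12.5, add what the sample can exclude (for example, 0/94 excludes rates above 3.8%), and state the sidedness and method behind the 80% power at 9.1%.

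No non-inferiority margin is needed for this. Data collection, sample size and clinical rules are unchanged, and the biomarker and symptom intervals come from models already planned. The downside is that the safety conclusion becomes less categorical.

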## 2.0 BACKGROUND AND HYPOTHESES

### 2.1 **BC risk in radiation exposed childhood, adolescent, and young adult cancer (CAYAC) survivors.**

Radiation therapy (RT) is a cornerstone of treatment for several cancers that commonly occur during childhood, adolescence, and young adulthood. These include Hodgkin lymphoma (HL), non-Hodgkin lymphoma (NHL), Ewing sarcoma (ES), rhabdomyosarcoma, and Wilms tumor. Occasionally other lymphomas and sarcomas are treated with RT as well. RT for HL and NHL with bulky mediastinal involvement typically involves the chest. Among sarcomas of the upper extremities treated with RT, the radiation port may include the axilla, from which there may be scatter to the chest wall. While RT for Wilms tumor typically involves the abdomen, occasionally the radiation RT port may cross the diaphragm. RT is also delivered as part of the total body irradiation (TBI) conditional regimen for hematopoietic cell transplant (HCT), commonly used in the treatment of acute leukemia and as salvage therapy for germ cell tumors and other solid cancers that may occur in children, adolescents, and young adults.

Over the past 20 years, the incidence of childhood cancer has increased modestly from 11.5 cases per 100,000 children in 1975 to 14.8 per 100,000 in 2004 [3]. During this same time, however, death rates dramatically declined for most childhood cancers. For instance, 5-year survival rates for all childhood cancers combined increased from 58% in

1975–77 to 80% percent in 1996–2003 [3]. This trend has been attributed to therapeutic advances, including the use of RT.

For example, until the late 1980s, standard treatment of pediatric patients with HL involvement of mediastinal lymph nodes (constituting three-quarters of patients) included RT at a dose of 40 to 45 Gy radiation to the “mantle” field, which encompasses the primary lymph node regions of the neck, supraclavicular, infraclavicular, axillary, and mediastinal areas (Figure 1) [2]. With this treatment, nearly 90% of patients diagnosed with HL, and treated with mantle radiation prior to age twenty survived beyond five years [3]. After the first late effects of HL therapy, such as growth deformities, began to be recognized, the field and dose of RT was reduced and radiation was combined with chemotherapy [4]. The combined modality approach has maintained high cure rates, such that late effects like second malignant neoplasm (SMNs) and cardiovascular disease now account for more deaths than those attributed to progressive HL [5]. In fact, of approximately 120,000 HL survivors in the United States, SMNs are the leading cause of death, with BC the most frequent solid tumor occurring in females treated for HL [6].

[figure not shown]
[figure not shown]
[figure not shown]
[figure not shown]
*Magnitude of risk of BC after radiation exposure:* Reported standardized incidence ratios (SIR) or relative risks (RR) for BC in this population range from 11.6 to 136.0, with the highest risk estimates generally from relatively smaller single institution studies [7-9]. From the single institution study with the largest number of women exposed to chest RT prior to 21 years of age (N=307), Wolden *et al* reported a RR of 26.2 [10]. A population-based study by Metayer *et al* reported a RR of 11.6 derived from 2,737 women who were diagnosed with HL prior to 21 years of age identified from nine U.S. NCI SEER registries and selected European countries [11]. Within this cohort, 62 girls and young women diagnosed between ages 10 and 21 subsequently developed BC. Another population-based study, the British Childhood Cancer Survivor Study (British CCSS), which included 16 cases of BC among 383 women who were treated for HL prior to 15 years of age [12], reported a similar SIR of 13.3. In contrast, in an international population-based study, Maule *et al* reported a SIR of 20.9 and an absolute excess risk of 40.6 based on 6 cases of BC that developed in 422 women with a prior diagnosis of HL occurring before age 15 [13]. Bhatia *et al* from the multi-institutional Late Effects Study Group (LESG) reported an excess risk of 55.5 based on 29 cases of BC among 480 women diagnosed with HL prior to age 17 [14]. On the other hand, Kenney and colleagues reported an SIR of 24.7 in women who were treated for a pediatric cancer with chest RT prior to age 21 from the 26-institution U.S. Childhood Cancer Survivor Study (CCSS) [15]. With 95 cases of BC among 6,068 female pediatric cancer survivors, this study had a significantly larger number of women with BC, and thus may provide a more robust estimate. In addition, the risk estimate from the CCSS study included all pediatric cancers prior to BC, with a consequent heterogeneity of radiotherapy doses and fields, while the other risk estimates were based only on HL survivors. Thus, it is clear that the risk of BC is elevated in all radiation-exposed pediatric cancer survivors.

*Long latency between radiation exposure and diagnosis of BC:* The risk of BC does not begin to increase until approximately 8 years after chest RT, and the median age at BC diagnosis is 32 to 35 years, based on the LESG and CCSS studies [14, 15]. The British CCSS reported that by twenty-five years of follow-up, the cumulative risk of BC was 12.2%.

*Risk of BC with attained age:* Both the LESG and CCSS studies reported cumulative incidence of BC to be 13.9% and 12.9% by age 40 and 20% and 22% by age 45, respectively. Cumulative incidence rates reported by Travis *et al* ranged from 4.1% to 39.6% by age 30, depending on the age at diagnosis and amount of radiation received

[16]. For perspective, among *BRCA1* or *BRCA2* gene mutation carriers, the estimated cumulative incidence of BC at age 30 ranges from 1-5% and at age 40 ranges from 10-19% [17-20]. Thus, the risk for developing BC among HL survivors appears to exceed that of *BRCA* mutation carriers, especially before age 30 (4-40% in HL survivors compared to 1-5% in *BRCA* carriers). For survivors of other cancers, the risk appears to be elevated approximately 2-fold, similar to the degree of elevated risk for which standard-dose tamoxifen is typically offered. Importantly, in none of the studies of women treated with chest RT was a plateau of BC risk with increasing interval of follow-up observed (Figure 7, page 14).

*Risk modification by radiation dose, age, endogenous hormones, and family history:* Bhatia *et al* demonstrated preliminary evidence for an increasing risk of BC with a radiation dose of 26 Gy or more [14]. This has been confirmed by the CCSS, where a clear dose-response relationship is evident between the dose of RT to the chest and the risk of subsequent BC down to exposures of 15 Gy (Figure 2) [15]. Using a case-control design, Travis *et al* confirmed that BC risk was related to the dose of RT [21]. Following 23.1-37.1 Gy and 37.2-61.3 Gy radiation delivered to the site where a secondary BC later appeared, the RR was 8.5 and 10.5, respectively. In Figure 3, Travis *et al* clearly demonstrates that BC risk increases with dose of radiation and latency from exposure to radiation. A novel finding in this study was a protective effect of exposure to an alkylating agent (AA) or radiation to the ovaries with respect to the development of BC following chest RT (Figure 3). While still having an increased BC risk compared to population rates, those who received chest RT plus an AA or pelvic RT had a significantly lower BC

risk than women treated with chest RT alone. Hill *et al* reported that parity appeared to contribute to BC risk among women who did not receive ovarian-damaging therapy [22]. The finding of a reduced risk in women with pelvic RT was confirmed in the CCSS (Figure 4) [15]. The findings across these studies highlight that endogenous estrogen may modify BC risk in this population. Although both the CCSS study and the report by Travis *et al* found that a family history (FH) of breast or ovarian cancer was associated with an increased risk of secondary BC among CAYAC survivors exposed to chest RT (Figure 4) [15, 22], multiple regression models suggested that additional risk of BC after chest RT is unlikely to be larger among women with a FH of breast or ovarian cancer. Lastly, age at radiation exposure also is an important risk factor, with chest RT exposures prior to age 30 impacting most significantly on BC risk (Figure 5).

A synergistic effect between radiation and estrogen exposures was, in fact, originally described in a rat mammary carcinoma model in the 1970s [23]. This effect was related to hormonal dose [24], radiation dose [25], and age at radiation exposure [26]. All of these laboratory observations are consistent with the epidemiologic observations among radiation exposed CAYAC survivors described above. Therefore, estrogen appears to play an important role in the etiology of radiation-induced BCs, and an estrogen-blocking intervention is expected to prevent radiation-induced BCs.

**2.2 Current options for BC risk reduction.** In other populations with an elevated risk for developing BC, such as women with a family history of BC, those with reproductive risk factors associated with BC, women with a personal history of premalignant breast disease, or those who are *BRCA* carriers, risk reduction strategies have included surgical and pharmacologic interventions [27].

*Surgical interventions:* Prophylactic bilateral mastectomy is associated with a 90-95% reduction in risk in women with familial BC [28]. This risk reduction measure has been the intervention of choice in women at high risk for BC who also have high cancer worry; however, not all women feel comfortable with this surgical option [29]. Alternatively, a 50-70% reduction in BC risk has been observed with bilateral oophorectomy, in addition to a 80-90% reduction in ovarian cancer risk [30, 31]. Prophylactic bilateral salpingo-oophorectomy (BSO) is a standard recommendation for women with a germline *BRCA1* or *BRCA2* mutation after they have completed childbearing primarily because of the associated elevated ovarian cancer risk. However, due to increased risks of osteoporosis, dyslipidemia and cardiovascular disease resulting from early menopause, BSO is not a procedure that is recommended for BC risk reduction in other patient populations in which an elevated BC risk is not associated with an elevated ovarian cancer risk (eg. carriers of germline mutations in *PTEN* or *TP53*) [32].

*Pharmacologic interventions:* Tamoxifen, a synthetic selective estrogen receptor modifier (SERM), was demonstrated to decrease the risk for BC by approximately 50% in women at moderately increased risk for developing BC as defined by the Gail model, a validated statistical tool which estimates the risk of developing BC by age 90 and within 5 years based on the following risk factors: current age, age at menarche, age at first birth, number of first degree relatives with BC, and number of prior breast biopsies [33, 34]. This finding led to the approval of tamoxifen for BC risk reduction by the Food and Drug Administration (FDA) in 1998. Raloxifene, another agent in the SERM class originally developed for the treatment of postmenopausal osteoporosis, was also noted to be associated with dramatic reductions in breast cancer risk [35, 36]. The NSABP P-2 Study of Tamoxifen and Raloxifene (STAR) trial compared the relative efficacy of the two SERMs, tamoxifen and raloxifene, for BC prevention in postmenopausal women at

moderately elevated risk for BC and found that raloxifene was equivalently efficacious but was associated with a better side effect profile [37]. However, raloxifene has only been tested in postmenopausal women, and is only FDA approved for either osteoporosis or BC prevention in women who have reached menopause.

Aromatase inhibitors (AI) are more efficacious and are better tolerated than tamoxifen in the treatment of postmenopausal hormone receptor positive BC. In the adjuvant setting, a reduction in the incidence of contralateral BC was observed for all three currently marketed AIs, anastrozole, letrozole, and exemestane [38-40], suggesting that AIs may also be useful for BC chemoprevention. Clinical trials are now underway to test this hypothesis; however, their efficacy is limited to postmenopausal women, since negative feedback to the hypothalamus and the pituitary further drives, rather than suppresses, ovarian estrogen production in premenopausal women.

Therefore, the only FDA-approved BC chemopreventive option in premenopausal women is tamoxifen. However, tamoxifen administered at a 20 mg daily dose is associated with uterine malignancies, stroke and venous thromboembolism. Although these adverse events occurred in less than 1% of the nearly 13,000 women studied, concerns about these side effects have been a deterrent to the widespread use of tamoxifen at a standard dose of 20 mg for BC chemoprevention. In addition, tamoxifen at this dose results in vasomotor and gynecological symptoms in approximately two-thirds of users, which can interfere with patient compliance with their use [33].

These concerns led some investigators in Italy to evaluate lower doses of tamoxifen in a four-arm double-blind placebo-controlled randomized trial of 210 healthy postmenopausal women, hoping to find a dose that would be better tolerated yet still efficacious for breast cancer risk reduction [41]. Participants were randomized to one of four treatment arms: 1) tamoxifen at 1 mg/day and a weekly placebo, 2) a daily placebo and tamoxifen at 10 mg/week, 3) tamoxifen at 5 mg/day and a weekly placebo, or 4) both daily and weekly placebos for 12 months. Plasma insulin-like growth factor 1 (IGF-1), which is positively correlated with BC risk, was the primary endpoint, evaluated before and after the 12-month treatment. Secondary endpoints included MBD, IGF binding protein-3 (IGFBP-3), fibrinogen, antithrombin-III (AT3), C-telopeptide (CTX), and endometrial proliferation assessed by Pipelle biopsy. MBD is positively correlated with BC risk, while IGFBP-3 is negatively correlated with BC risk. Along with IGF-1, they served as surrogate endpoints of efficacy. Fibrinogen and AT3 are markers of clotting risk, CTX, which is positively correlated with bone resorptive activity, is a marker for osteoporosis risk, and endometrial proliferation is a marker of uterine cancer risk. Collectively, these were safety endpoints in the trial. The investigators reported a significant decrease in IGF-1 in all tamoxifen arms relative to placebo ( $p = 0.005$ ), with the greatest change observed in the 5 mg/day treatment arm ( $p = 0.019$ ). Low-dose tamoxifen also lowered MBD and increased IGFBP-3, with optimal effects observed in the 5 mg/day arm. These findings all consistently suggest that 5 mg/day dosing is the most effective dose schedule of low-dose tamoxifen. No significant change was observed with CTX, suggesting that low-dose tamoxifen does not adversely affect bone health. Interestingly, a significant decrease in AT3 ( $p = 0.006$ ), particularly with the 5 mg/day dose schedule, was also seen, suggesting that low-dose tamoxifen may be associated with a lower clotting risk than even placebo. While there was an association between low-dose tamoxifen and endometrial thickness, no association was found with endometrial proliferation measured with Ki67 expression. In fact, Ki67 was lowest in patients receiving the 5 mg/day dose, suggesting that low-dose tamoxifen at that dose would likely not be associated with an increased risk of endometrial carcinoma as is observed with standard dose tamoxifen. Also, menopausal symptoms were not

significantly worsened by low-dose tamoxifen. In summary, low-dose tamoxifen, especially when taken at 5 mg/day is associated with a decreased risk of BC and without the typical adverse effects associated with standard dose tamoxifen.

A follow-up trial randomized 235 premenopausal women with intraepithelial neoplasia (IEN) or 5-year Gail risk >1.3% to tamoxifen 5 mg daily versus fenretinide 200 mg daily in a 2x2 factorial fashion for two years. As with the previous study, a two-year course of 5 mg daily of tamoxifen was associated with a significant decrease in MBD and IGF-1 [42, 43]. Unlike the first study, the second study included long-term follow-up for outcomes, and after a median of 38 months, 24 women developed BC [42]. Trends toward lower annual BC rates were observed in the tamoxifen and fenretinide single agent arms, compared to placebo (2.0, 2.7, and 5.4 per 100, respectively) [42]. Based on the findings in both studies, we believe that a 5mg daily dose of tamoxifen will be a better tolerated, efficacious chemopreventive option for a mixed population of pre- and post-menopausal high-risk women.

A preclinical tamoxifen chemoprevention trial resulted in both decreased incidence and prolonged latency of radiation-induced mammary carcinomas [44]. In this study, female Sprague-Dawley rats were exposed to 300, 500, or 900 cGy total body irradiation (TBI) vs sham and 30 days later half of animals in each radiation treatment group received tamoxifen. Tumor formation after 12 months of follow-up was completely inhibited, and tumor incidence after 24 months follow-up was reduced by 50% in all TBI groups combined. The tamoxifen intervention was most efficacious among animals who received 300 or 500 cGy TBI.

Thus, there is strong preclinical, epidemiologic, and clinical trial evidence supporting our choice tamoxifen to reduce BC risk among young predominantly premenopausal female radiation-exposed HL survivors.

- 2.3 **Clinical characteristics of radiation-associated BC.** Little information exists regarding clinical characteristics and outcomes of women diagnosed with BC after radiation exposure. In the only peer-reviewed published study evaluating BC outcomes after RT for prior lymphoma – a single institution experience described by Sanna *et al* [45], BCs in 53 women with either a prior diagnosis of HL or NHL treated at the European Institute of Oncology were compared to sporadic BC cases treated at the same institution matched for age, year of diagnosis, stage, and hormone receptor status. The cases were not significantly different in terms of biologic features (eg. Her-2 expression), but there was a trend toward more lobular histology, higher grade, and higher Ki67 proliferation index in the lymphoma-associated breast cancers. Interestingly, Sanna and colleagues reported that in their patient sample, both 5-year disease free survival (54% versus 91% in controls) and overall survival (87% versus 99%) were statistically significantly decreased ( $p < 0.0001$  and  $p = 0.03$ , respectively) for BC diagnosed after lymphoma. Although no significant differences in medical and surgical therapy could be detected overall, anthracycline use was significantly lower among women with node-positive disease ( $p = 0.03$ ). In addition, significant differences in RT among the lymphoma survivors were observed, with over a third receiving intraoperative electron beam radiotherapy, compared to only 10% of controls ( $p = 0.0001$ ). Such treatment differences are likely due to concerns for toxicity due to prior treatment exposures, and probably underscore the differences in outcome, since histologic differences observed were minor. Regardless, the finding of worse clinical outcomes from secondary BC in lymphoma survivors provides a strong rationale to support the importance of finding ways to prevent this

disease in women who have survived HL, who are at enormously high risk for developing BC with limited ability to tolerate full treatment for BC, if it occurs.

Because the control group for the patient cohort described by Sanna and colleagues was matched for hormone receptor status, nothing can be said about ER expression in HL-associated BC compared to sporadic BC. Only three studies have reported hormone receptor expression and are listed in Table 1. In all three studies, ER expression data was available on less than half of BC cases. Nevertheless, the two larger studies, including the CCSS study and one case series from Stanford, report a similar proportion of ER-expressing breast tumors among cases of secondary BC after HL compared to what would be expected with sporadic BC [10, 15]. Furthermore, several animal models have demonstrated no reduction in ER expression among radiation-induced rodent mammary tumors [46, 47].

[figure not shown]
In addition, as reviewed above, it has been observed that CAYAC survivors who had received chest RT plus an alkylating agent or radiation to the ovaries, both of which are associated with premature menopause, had a significantly lower BC risk than CAYAC survivors treated with chest RT without these exposures [15, 16]. Similarly, surgical menopause after BSO has been shown to decrease sporadic and BRCA-associated BC [30, 31]. Thus, it is expected that a hormonal intervention would be appropriate for chemoprevention of radiation-associated BC, just as it is for sporadic and BRCA-associated BC [48].

